5.3.2. Estimand

An estimand is a precise definition of the primary targeted treatment effect defined by the following 5 attributes: Study intervention by Week 12, Population, Variable (endpoint), Intercurrent events (ICEs) and corresponding strategies, and Population-level summary.

There are 2 co-primary estimands in this study corresponding to the 2 co-primary endpoints defined in Section 5.3.1.

Primary Trial Objective: to evaluate the clinical and endoscopic efficacy of guselkumab in participants with moderately to severely active Crohn's disease.

Estimand Scientific Question of Interest: What is the proportion of participants achieving clinical remission at Week 12 and the proportion of participants achieving endoscopic response at Week 12, and thus considered to have benefited from guselkumab versus placebo?

5.3.2.1. Co-primary Estimands

Co-Primary Estimand of Clinical Remission at Week 12 (Estimand 1)

Treatment by Week 12:

Experimental: Combined guselkumab CCI induction dose group (ie, both guselkumab groups who received CCI at Weeks 0, 4, and 8)

Control: Placebo SC q4w (Weeks 0, 4, and 8)

Population: Participants with moderately to severely active Crohn's disease

Variable (Endpoint):

A binary response variable (response/nonresponse) where response is defined as achieving CDAI score <150 at Week 12 without experiencing any of the ICEs in categories 1-3 and 5 as outlined below prior to the Week 12 visit.

Intercurrent events and corresponding strategies:

ICE Identifier	ICE Description	Corresponding Strategy
1	A Crohn's disease-related surgery (with the exception of minor procedures such as drainage of a superficial abscess or seton placement, etc.)	Composite
2	A prohibited change in Crohn's disease medication (See Appendix 2)	Composite
3	Discontinuation of study intervention due to lack of efficacy or an AE of worsening of Crohn's Disease	Composite
4	Discontinuation of study intervention due to COVID-19 related reasons (excluding COVID-19 infection) or regional crisis	Treatment Policy
5	Discontinuation of study intervention due to COVID-19 infection or for reasons other than those specified in ICE categories 3 and 4.	Composite

The composite strategy assesses the treatment effects not only based on the variable measurements, but also based on ICEs. This estimand acknowledges that having an ICE in categories 1-3 and 5 is an unfavorable outcome. For participants experiencing ICE category 4, the treatment policy strategy considers the occurrence of ICE category 4 is irrelevant in defining the treatment effect.

Population-level summary:

Difference in proportions of responders (according to the **Variable** defined above) between the combined guselkumab group and the placebo group.

Co-Primary Estimand of Endoscopic Response at Week 12 (Estimand 2)

Treatment by Week 12:

Experimental: Combined guselkumab CCl induction dose group (ie, both guselkumab groups who received CCl at Weeks 0, 4, and 8)

Control: Placebo SC q4w (Weeks 0, 4, and 8)

Population: Participants with moderately to severely active Crohn's disease

Variable (Endpoint):

A binary response variable (response/nonresponse) where response is defined as achieving endoscopic response (\geq 50% improvement from baseline in SES-CD score) at Week 12 without experiencing any of the ICEs in categories 1 to 3 and 5 as outlined above prior to the Week 12 visit.

Intercurrent events and corresponding strategies:

The same ICEs and corresponding strategies that are specified for the co-primary endpoint of clinical remission at Week 12 will be used.

Population-level summary:

Difference in proportions of responders (according to the **Variable** defined above) between the combined guselkumab group and the placebo group.

5.3.2.2. Supplementary Estimands for the Co-Primary Endpoints

In these supplementary estimands, all intercurrent events defined above for the co-primary estimands are addressed by the **composite strategy**. The supplementary estimands for the co-primary endpoints acknowledge that having an intercurrent event is an unfavorable outcome. The components of the supplementary estimands are the same as those for the primary estimands (estimands 1 and 2) with the exception of the Variable, which is described as follows:

Supplementary Estimand of Clinical Remission at Week 12 (Estimand 3)

Variable (Endpoint): A binary response variable (response/nonresponse) where response is defined as achieving CDAI score <150 at Week 12 without experiencing any of the ICEs in categories 1-5 prior to the Week 12 visit.

Supplementary Estimand of Endoscopic Response at Week 12 (Estimand 4)

Variable (Endpoint): A binary response variable (response/nonresponse) where response is defined as achieving endoscopic response (\geq 50% improvement from baseline in SES-CD score) at Week 12 without experiencing any of the ICEs in categories 1-5 prior to the Week 12 visit.

5.3.3. Analysis Methods

5.3.3.1. Estimator (Analysis) of the Co-primary Estimands

The analyses of the co-primary estimands will be based on the FAS, which includes all randomized participants who received at least 1 (partial or complete) dose of study intervention. Participants will be analyzed according to the intervention group to which they were randomized regardless of the study intervention they actually received.

Regarding the ICE strategies, for the treatment policy strategy, the associated ICE event will be ignored, and any data observed after the associated ICE event will be used for the analysis. After accounting for the treatment policy strategy, any missing data will be handled by the missing data rules described below.

If the CDAI score cannot be calculated based on the main approach (Section 5.3.1) at a visit, the CDAI score will be considered missing for that visit. Participants who have a missing CDAI score at Week 12 after accounting for the ICE strategies will be considered not to have achieved clinical remission at Week 12 (i.e., Nonresponder Imputation (NRI)).

For the co-primary endpoint of endoscopic response at Week 12, the SES-CD score will be calculated based on the main approach (Section 5.3.1). If the SES-CD score is missing at Week 12 after accounting for the ICE strategies, the participant will be considered not to have achieved the endpoint of endoscopic response at Week 12 (i.e., NRI).

For testing of the co-primary endpoints, the efficacy of the induction dose of guselkumab versus the placebo group will be compared. The two guselkumab groups that are randomized to receive an identical guselkumab induction dose regimen through Week 12 will be combined for these comparisons.

Summaries of the proportion of participants that achieve each co-primary endpoint and the associated 95% confidence interval by treatment group, along with the adjusted treatment difference between guselkumab group and the placebo group, as well as the associated 95% confidence interval, will be presented for each co-primary endpoint. Guselkumab versus placebo will be compared for the co-primary endpoints using a 2-sided Mantel-Haenszel test (Common Risk Difference Test using Mantel-Haenszel stratum weights) at a significance level of 0.05. Specifically, the adjusted treatment differences will be in terms of the common risk difference using Mantel-Haenszel stratum weights and the variance will be based on the Sato variance estimator. The stratification variables used are baseline CDAI score (\leq 300 or >300), baseline SES-CD score (\leq 12 or >12), and BIO-Failure status (Yes or No).

To control the Type I error rate, a fixed sequence testing approach will be used for the co-primary endpoints. In particular, clinical remission at Week 12 will be tested first, followed by the testing of endoscopic response at Week 12.

5.3.3.2. Estimator (Analysis) for the Supplementary Estimands of the Coprimary Endpoints

The same estimators used for the co-primary estimands will be used for these supplementary estimands 3 and 4, with the exception that the rules for the treatment policy strategy will no longer apply. All ICEs for the supplementary estimands are addressed by the composite strategy. After accounting for the ICE strategies, participants whose responder status is missing (i.e., missing clinical remission/endoscopic response status at Week 12) for a co-primary endpoint will be considered to be a nonresponder for that co-primary endpoint.

5.3.4. Subgroup Analyses

For subgroup analyses, the analysis sets are based on the FAS. Subgroup analyses based on demographics, baseline disease characteristics, and baseline and previous use of medications for Crohn's disease (including BIO-Failure status) will be performed when the number of participants in each subgroup permits (See Section 5.7.7 for definition of subgroups).

For each of the subgroups, the rate (risk) difference of induction dose of guselkumab vs. placebo and the associated p-values and 95% confidence intervals will be provided using forest plots. The difference in proportions, p-values and confidence intervals will be provided based on the same model specified in Section 5.3.3.1. The subgroup analysis on BIO-Failure status, baseline CDAI score (\leq 300 or >300), or baseline SES-CD score (\leq 12 or >12) will not include the corresponding stratification variable.

Using the co-primary estimands, an analysis of the co-primary endpoints will be performed for each region, country and investigator site. This analysis will be descriptive and statistical testing will not be applied.

5.3.5. Sensitivity Analyses

The following sensitivity analyses will be based on varying assumptions of the missing data.

5.3.5.1. Tipping Point Analysis Based on Multiple Imputation with Bernoulli Draws

A sensitivity analysis will be performed using a tipping point analysis with Bernoulli draws to impute missing clinical remission status at Week 12 and missing endoscopic response status at Week 12 after the intercurrent event rules have been applied, when the number of missing participants (after accounting for the ICE strategies) is >5% in any treatment group. This tipping point analysis involves the following distinct steps:

1. Some p will be assumed for each treatment group's response rate, which could vary by treatment group. The response status (Yes/No) for participants with a missing response will be imputed based on a Bernoulli distribution of p. This will be repeated n times (e.g., 200 times) to generate n multiple imputations.

2. Guselkumab versus placebo will be analyzed for the co-primary endpoints in terms of the common (overall) risk difference using Mantel-Haenszel stratum weights, and the variance will be based on the Sato variance estimator. The associated 2-sided Mantel Haenszel test (Common Risk Difference Test) at a significance level of 0.05 will be used to compare guselkumab group to placebo while adjusting for the stratification factors.

3. The results from the imputed data sets will then be combined to produce inferential results based on Rubin's rule.

The analysis will be repeated for a range of values for p (for example, 0% to 100% in increments of 10%, for the placebo and the guselkumab group independently). This tipping point analysis will allow for assumptions about the response rates in the two arms to vary independently; furthermore, it will include scenarios where imputed missing values on guselkumab have worse outcomes than missing values on placebo.

5.3.5.2. Missing at Random (MAR) MI (Multiple Imputation)

This sensitivity analysis will evaluate the co-primary endpoints (estimands 1 and 2) when all missing data (after accounting for ICE strategies) is imputed by MAR MI rather than NRI. Data that is missing, after accounting for the ICE strategies, include data after discontinuation of study intervention for participants with ICE 4 who do not have observed data at Week 12.

Multiple imputation (MI) as described below will be used for imputing missing data (after accounting for the ICE strategies) under the assumption that the data are missing at random (MAR), and binary responses will be obtained from the imputed scores of CDAI and SES-CD.

Variable		MI specifications
CDAI at Week 12	Multiple imputation with monotone regression of total scores	 MIdataset1 (N=200, Seed=4362478) Imputation variables: CDAI at Week 12 Ancillary variables: Treatment group, Baseline CDAI, randomization stratification factors (except categorical Baseline CDAI)
SES-CD at Week 12	Multiple imputation with monotone regression of total scores	 MIdataset1 (N=200, Seed=4362478) Imputation variables: SES-CD Total Score at Week 12 Ancillary variables: Treatment group, Baseline SES-CD, randomization stratification factors (except categorical Baseline SES-CD)

Multiple Imputation Methods for CDAI and SES-CD at Weeks 12

Repeat it 200 times, which results in 200 data sets. Each of the 200 resulting data sets will be analyzed in terms of the common (overall) risk difference using Mantel-Haenszel stratum weights and the Sato variance estimator. The associated 2-sided Mantel Haenszel test (Common Risk Difference Test) at a significance level of 0.05 will be used to compare guselkumab group to placebo while adjusting for the stratification factors: baseline CDAI score (\leq 300 or >300), baseline SES-CD score (\leq 12 or >12), BIO-Failure status (Yes or No). The results from the 200 data sets will be combined to produce inferential results based on Rubin's rule.

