Administrative								
Inclusion/exclusion criteria	X							
Review medical history	X							Verify any additional changes since medical history review at screening visit.
Study Intervention Administration								
Randomization	X							Randomization should be performed within approximately 5 weeks after screening/informed consent signing.
Dispense study intervention	X	X	X	X	X	X	X	
Administer study intervention	X	X	X	X	X	X	X	All procedures/assessments described in this SoA table are to be completed prior to study intervention administration on site, unless otherwise specified. PRO assessments should be completed first, followed by the C-SSRS assessment, and then any other clinical procedures, tests, or consultations.
Study intervention accountability	X	X	X	X	X	X	X	
Safety Assessments								
Physical examination	X	X	X	X	X	X	X	A targeted physical examination will be performed (see Section 8.2.1).
Vital signs	X	X	X	X	X	X	X	Includes temperature, pulse/heart rate, respiratory rate, and blood pressure. Must be obtained prior to and approximately 30 minutes after the SC injection.
Urine pregnancy test	X	X	X	X	X	X	X	Must be performed before every study intervention administration in female participants of childbearing potential.
TB evaluation/other infection assessment	X	X	X	X	X	X	X	If TB is suspected at any time, study intervention should be withheld and an immediate and thorough investigation should be undertaken. More information on TB evaluation is provided in Section 8.2.10.
Injection-site evaluation	X	X	X	X	X	X	X	An injection-site reaction is any adverse reaction at an SC study intervention injection site. Injection sites will be evaluated for reactions, and any injection-site reaction will be recorded as an AE.
C-SSRS	Х	X	X	X	X	X	Х	The C-SSRS should be completed after all PRO assessments and before any other tests, procedures, or other consultations to prevent influencing participant perceptions. The investigator or trained study site personnel will interview the participant and complete the C-SSRS.
Efficacy Assessments								
Collect and review Symptom and Health Diary (CDAI, BSFS, AP-NRS)	X	X	X	X	X	X	X	Diary information should be completed daily, and participants should bring their diaries to each on-site visit. The daily diary includes patient-reported data for the CDAI, BSFS, and AP-NRS.

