5.1.1. Visit Windows

Unless otherwise specified, nominal scheduled visits (described in SoA of the protocol) will be used for over time summaries and listings with no visit windows applied. However, the Unscheduled Visit (USV), Study Intervention Discontinuation (SID) and Final Efficacy and Safety (FES) visits will be slotted to scheduled visits according to the following mapping rules except for SES-CD endpoint:

- 1. Assign a visit number to USV, SID or FES visit based on the Study Day as illustrated in Table 2
- 2. If USV, SID or FES visit falls in the window of a scheduled visit and there are not already data for the scheduled visit, assign the scheduled visit number to the USV, SID or FES visit. If there are already data for a same scheduled visit, those data will be used in lieu of the USV, SID or FES visit data.

Week 4	Day 2-42
Week 8	Day 43-70
Week 12	Day 71-98
Week 16	Day 99-126
Week 20	Day 127-154
Week 24	Day 155-182
Week 28	Day 183-210
Week 32	Day 211-238
Week 36	Day 239-266
Week 40	Day 267-294
Week 44	Day 295-322
Week 48	Day 323-350
Week 52	Day 351-378
etc.	
Week 96	Day 659-686

Table 2: SID/FES/Unscheduled Visit Slotting

More frequent measurements are taken for other endpoints compared to endoscopic assessments taken only at Weeks 0, 12, 48, and 96.

For SES-CD endpoint using a wider window: +/- 4 weeks

Week 12: Days 57 to 113

Week 48: Days 309 to 365

Week 96: Days 645 to 701

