5.3. Co-Primary Endpoints Analysis

5.3.1. Definition of Endpoints

The co-primary endpoints are:

- Clinical remission at Week 12
- Endoscopic response at Week 12

Clinical remission is defined as a CDAI score <150.

Endoscopic response is defined as \geq 50% improvement from baseline in Simple Endoscopic Score for Crohn's Disease [SES-CD].

CDAI score

The CDAI is a validated multi-item measure of severity of illness derived as a weighted sum of 8 different Crohn's disease-related variables. These 8 variables are:

- extra-intestinal manifestations
- abdominal mass
- weight
- hematocrit
- use of antidiarrheal drug(s) and/or opiate
- total number of liquid or very soft stools
- abdominal pain/cramps
- general well-being.

Calculation of the CDAI score:

Two approaches to calculating the CDAI score are provided below. The main approach will be used for the analysis of all endpoints that include the CDAI; of particular note is that this main approach is used for the co-primary and secondary endpoints that involve the CDAI. Additional analyses of co-primary and secondary endpoints that involve the CDAI will also be provided using the alternative approach.

Main approach

The last 3 components of the CDAI score listed above are scored over 7 days by the participant on a diary card. For the total number of liquid or very soft stools, abdominal pain/cramps, and general well-being, if only 5 days or 6 days of data are available for the calculation, the weights of 7/5 and 7/6, respectively, will be used for the calculation; if the values are recorded for less than 5 days, the component will not be calculated.

The CDAI score calculation algorithm is presented in Section 10.8 Appendix 8 of the study protocol. At each timepoint, the CDAI score will only be calculated if \geq 4 of the 8 components are available. If the CDAI score cannot be calculated (ie, <4 components available), the CDAI score will be considered missing. When at least 4 of the 8 components are available, any missing components will be imputed by carrying forward the last non-missing value for that component.

Alternative approach

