5.5.3. Analysis Methods

Through Week 24

Exploratory endpoints through Week 24 (eg, clinical remission, clinical response) will be tested regardless of the significance of the co-primary and secondary endpoints; the testing of these exploratory endpoints through Week 24 will not be controlled for multiplicity. Nominal p-values will be presented.

Descriptive statistics (i.e., N, mean, median, SD, IQ range, minimum, and maximum) will be used to summarize continuous variables. Counts and percentages will be used to summarize categorical variables. Graphical data displays (e.g., line plots) may also be used to summarize the data.

The estimand approach and analysis methods specified in Sections 5.4.2.1 and Section 5.4.3.1 for the secondary endpoints will apply to binary endpoints. The ICEs are the same as those specified in Sections 5.4.2.1

For continuous endpoints, the attributes of the estimands will be the same as those specified for the secondary endpoints relative to **Study Intervention**, **Population**, and **ICEs**. If a participant has an ICE in categories 1-3, 5, or 6, baseline values will be assigned from the point of ICE onward. For participants experiencing ICE 4, the associated ICE event will be ignored and any data observed after the associated ICE event will be used for the analysis.

Continuous efficacy endpoints that are collected at multiple post baseline time points through a given visit will be compared using a Mixed Model Repeated Measures (MMRM). The model will include all available data from all treatment groups through that visit for assessing efficacy.

The MMRM model will be used to test the difference between the combined guselkumab group or each guselkumab group versus the placebo group. This model relies on the MAR assumption for the missing responses. Under the assumption of MAR, the missing data will be accounted for through correlation of repeated measures in the model.

The explanatory variables of the MMRM model will include treatment group, visit, applicable baseline score, BIO-Failure status (yes, no), baseline CDAI (\leq 300 or > 300), baseline SES-CD (\leq 12 or > 12), an interaction term of visit with treatment group, and an interaction term of visit with applicable baseline score. Change from baseline in CDAI endpoints will not include CDAI strata in the model, as the baseline CDAI is already included as a factor.

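### The MAR imputation of Week 12 CDAI leaves out the Week 4 and Week 8 CDAI, so this sensitivity analysis rests on a more restrictive missing-data assumption than the data require; the likely effect is small

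*SAP*

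**What the plan says.** SAP 5.3.5.2 describes the method for Week 12 CDAI as "Multiple imputation with monotone regression of total scores". The only variable imputed is the Week 12 total. The predictors are given as "Ancillary variables: Treatment group, Baseline CDAI, randomization stratification factors", with the categorical CDAI stratum removed because continuous baseline CDAI is already in the model. That leaves arm, baseline CDAI, the SES-CD stratum and BIO-Failure status. No post-baseline CDAI appears.

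Protocol Section 1.3, Table 2 has the row "Collect and review Symptom and Health Diary (CDAI, BSFS, AP-NRS" marked at every visit from Week 0 to Week 24, including Weeks 4 and 8. Weight and hematology are scheduled at the same visits. SAP 5.5.2.1 analyses change in CDAI over time, so the intermediate scores will be derived in any case.

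Other SAP rules limit who reaches the imputation:

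- 5.3.2.1: "This estimand acknowledges that having an ICE in categories 1-3 and 5 is an unfavorable outcome".
- 5.3.1: if at least 4 of the 8 CDAI components are available, "any missing components will be imputed by carrying forward the last non-missing value for that component".
- 5.1.1: "If USV, SID or FES visit falls in the window of a scheduled visit and there are not already data for the scheduled visit", that visit takes the scheduled visit's number. For Week 12 the window is Days 71 to 98.
- 5.3.3.1: the co-primary analysis counts any remaining missing Week 12 CDAI as non-response.
- 5.3.5.1: the tipping point analysis runs only "when the number of missing participants (after accounting for the ICE strategies) is >5% in any treatment group".

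**The concern.** MAR is always conditional on the variables in the imputation model. Here, two participants in the same arm with the same baseline data receive the same imputation distribution for Week 12, even if one was close to remission at Week 8 and the other was worsening. If on-study CDAI influences who lacks a Week 12 score, the imputed remission rates are wrong by different amounts in the two arms, and the risk difference moves. If it does not, there is no bias, but precision is lost.

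The point has some practical weight because of the tipping point trigger. When residual missingness is 5% or less in every group, this multiple imputation is the only analysis in SAP 5.3.5 that varies the missing-data assumption. Two other analyses give partial cover: the supplementary estimand counts ICE 4 as non-response (5.3.3.2), and the alternative CDAI calculation applies stricter rules (5.3.6.1). Both still treat missing scores as non-response, so neither replaces an MAR analysis.

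**Working it through.** **Plan's own figures.** The documents give no figure for this imputation. The sample-size figures reproduce with a two-sided chi-square test at 0.05 and 212 versus 106: 15% vs 50% gives above 99.99% (stated >99%), and 13% vs 30% gives 93.85% (stated 94%). None of these depends on the imputation model.

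**Who is imputed.** ICE 1-3 and 5 are removed as non-response, and ICE 5 takes in every discontinuation not in ICE 3 or 4. What remains is ICE 4 (COVID-19 logistics or regional crisis) without Week 12 data, and participants with no intercurrent event whose Week 12 CDAI cannot be calculated. An attendee with the four components that are not summed from the diary (manifestations, mass, weight, hematocrit) already has a score, with any missing diary components carried forward.

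**Scale.** SE of the risk difference = 100 x sqrt(0.5 x 0.5/212 + 0.15 x 0.85/106) = 4.88 points.

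**Assumed inputs (none is in the documents).** Multivariate normal CDAI at baseline and Weeks 4, 8 and 12; baseline mean 300, SD 60, limited to 220-450. Correlations: baseline with W4, W8, W12 = 0.50, 0.40, 0.30; W4-W8 0.75; W4-W12 0.60; W8-W12 0.75. Remission cut-offs are set to the SAP rates of 50% and 15%. Missingness is logistic in standardized Week 8 CDAI.

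**Formula.** Shift = f_g x (imputed - true)_g - f_p x (imputed - true)_p, where f is the missing fraction and the bracket is the remission rate among the missing, as imputed from baseline and in truth.

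**Missing rates fixed separately by arm.** At 5% missing in each arm and log-odds 1.0 per SD, remission among the missing is 0.248 true and 0.481 imputed on guselkumab, and 0.042 true and 0.137 imputed on placebo:

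100 x [0.05 x (0.481 - 0.248) - 0.05 x (0.137 - 0.042)] = 100 x [0.01165 - 0.00475] = +0.69 points.

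| Missing, guselkumab/placebo | Log-odds +0.5 | +1.0 | +1.5 |
|---|---|---|---|
| 2%/2% | +0.13 | +0.28 | +0.40 |
| 5%/5% | +0.32 | +0.69 | +0.99 |
| 5%/2% | +0.51 | +0.98 | +1.33 |
| 2%/5% | -0.05 | -0.01 | +0.06 |
| 1%/5% | -0.18 | -0.24 | -0.24 |

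At log-odds 0 every shift is within 0.01. If missingness instead falls as CDAI rises (log-odds -0.5 to -1.5), the shifts are -0.45 to -0.93 at 5%/2% and +0.32 to +1.15 at 1%/5%.

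**One rule common to both arms.** If high CDAI drives absence, placebo, with higher CDAI, should lose more participants. The same correlations were used with a single intercept, a Week 8 treatment effect of 0.5 to 1.0 times the Week 12 effect, and log-odds 0.5 to 1.5:

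- 2% overall missing: about -0.12 to +0.15 points (0.15/4.88 = 3% of one SE).
- 5% overall missing: about -0.25 to +0.39 points (0.39/4.88 = 8% of one SE). Placebo missingness exceeds 5% in every one of these runs, so the tipping point analysis would also run.

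**A second set-up.** This used SD 95, Week 8-12 correlation 0.5 or 0.7, a common rule with slope 0.02 per CDAI point (0.02 x 95 = 1.9 log-odds per SD), and a Week 8 effect equal to the Week 12 effect. At 5% missing, the risk difference from baseline-only imputation was 34.64 against 35.10 with full data (-0.46), and 34.71 against 35.22 (-0.51). Its standard error was about 5.1, against 4.9 with Weeks 4 and 8 added. At 10% and 15% missing the estimate was low by 0.8-0.9 and 1.2 points, again at levels where the tipping point analysis would run.

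**With Weeks 4 and 8 in the model,** the shift is within 0.01 in the first set-up and within 0.1 in the second. That recovery is built in, because missingness was generated from Week 8 CDAI.

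**The case against.** The strongest reply is that this is a preference. The model is fully specified and valid under its stated assumption, it feeds one sensitivity analysis, and nothing else in the plan conflicts with it. The people who reach the imputation are mainly those absent for logistical reasons, and nothing in the documents suggests that such absences depend strongly on Week 8 CDAI. All of that stands, and it is why the point carries the lowest severity. It does not remove the point: better predictors are already collected and cost nothing to use.

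Three stronger readings are tempting, and the documents support none of them.

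- A reader might infer that the imputation favours guselkumab by 1.0 to 1.3 points, or 20% to 27% of one SE (0.99/4.88 and 1.33/4.88). With missingness that rises with CDAI and rates up to 5%, those values need missing rates that are equal in the arms or higher on guselkumab, together with strong dependence on Week 8 CDAI. The documents give no missing rates and no mechanism, and plausible inputs produce either sign.
- A reader might infer that the SAP contradicts itself, since its MMRM in 5.5.3 states: "Under the assumption of MAR, the missing data will be accounted for through correlation of repeated measures in the model". That model serves continuous exploratory endpoints. It shows that conditioning on earlier visits is feasible, not that 5.3.5.2 is inconsistent.
- A reader might extend the point to SES-CD. Endoscopy has no scheduled assessment between screening and Week 12, so no intermediate score is being left out.

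**Conclusion.** The specification gap is real and specific to CDAI. By conditioning only on arm and baseline data, SAP 5.3.5.2 assumes that missingness is unrelated to on-study CDAI given those variables, although CDAI at Weeks 4 and 8 is available to relax that assumption.

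The expected consequence is minor: a few tenths of a point at most under a common missingness rule with log-odds up to 1.5 and up to 5% missing, about half a point under steeper dependence, and nothing if missingness does not depend on on-study CDAI. The direction cannot be determined from the documents. These sizes rest on assumed correlations, missing rates and mechanisms. The co-primary test uses non-responder imputation and never calls this model, so no trial conclusion is at risk. Lowest severity.

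**What to change.** In SAP 5.3.5.2, for CDAI only, impute sequentially at Weeks 4, 8 and 12. Each step should use arm, baseline CDAI, the SES-CD and BIO-Failure strata, and all earlier CDAI values. Gaps that break the monotone pattern (for example Week 8 missing but Week 12 present) should first be filled by MCMC, or fully conditional specification used throughout. State that participants with ICE 1-3 or 5 remain non-responders. Keep the 200 imputations and Rubin's rule, and leave the SES-CD row as it is.

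If the Week 24 database lock has passed, keep the planned analysis and report this one beside it, labelled as additional.

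The cost is a few lines of SAP text and code. No new data are needed, and the primary analysis, sample size and alpha are unchanged.
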